**ACR20**

The ACR20 is a primary efficacy measure for which a patient must have at least 20% improvement in the following ACR Core Set values.

- TJC (68 joint count) and
- SJC (66 joint count) and
- An improvement of at least 20% in at least 3 of the following 5 assessments:
  - Patient's Global Assessment of Disease Activity
  - Patient's Assessment of Arthritis Pain
  - Patient's Assessment of Physical Function as measured by the HAQ-DI
  - Physician's Global Assessment of Disease Activity
  - Acute phase reactant as measured by CRP.

In this trial, ACR20 response calculations will use the HAQ-DI for the patient's assessment of physical function and CRP as the measure of acute phase reactant.

**ACR50 and ACR70**

ACR50 and ACR70 are defined in the same way as the ACR20 using at least 50% and 70% improvement, respectively.

**7.3.1.2 DAS28-ESR**

The DAS28-ESR is a measures of disease activity in 28 joints that consists of a composite numerical score of the following variables: TJC, SJC, or ESR, and Patient's Global Assessment of Disease Activity (57).

For DAS28-ESR, the 28 joints to be examined and assessed as tender or not tender for TJC and to be examined and assessed as swollen or not swollen for SJC include 14 joints on each side of the patient's body: 2 shoulders, 2 elbows, 2 wrists, 10 metacarpophalangeal joints, 2 interphalangeal joints of the thumb, 8 proximal interphalangeal joints, and 2 knees (58).

DAS28 will be derived using the following formulas from the DAS28 website (59):

$$DAS28 = 0.56 * \sqrt{(TJC28)} + 0.28 * \sqrt{(SJC28)} + 0.014 * GH + 0.70 * \ln(ESR)$$

Where:

- TJC28 = 28 joint count for tenderness
- SJC28 = 28 joint count for swelling
- $\ln(ESR)$  = natural logarithm of ESR
- GH = the general health component of the DAS (ie, Patient's Global Assessment of Disease Activity on a scale of 1 to 10 where 10 is maximal activity).

### 7.3.1.3 CDAI

The CDAI is calculated based on the following formula (46):

$$CDAI = SJC28 + TJC28 + GH + PGA$$

Where:

- TJC28 = 28 joint count for tenderness
- SJC28 = 28 joint count for swelling
- GH = the general health component of the DAS (ie, Patient's Global Assessment of Disease Activity on a scale of 1 to 10 where 10 is maximal activity).
- PGA = Physician's Global Assessment of Disease Activity on a scale of 1 to 10 where 10 is maximal activity

### 7.3.1.4 SDAI

The SDAI is calculated based on the following formula (46):

$$SDAI = SJC28 + TJC28 + GH + PGA + CRP$$

Where:

- TJC28 = 28 joint count for tenderness
- SJC28 = 28 joint count for swelling
- GH = the general health component of the DAS (ie, Patient's Global Assessment of Disease Activity on a scale of 1 to 10 where 10 is maximal activity).

- PGA = Physician's Global Assessment of Disease Activity on a scale of 1 to 10 where 10 is maximal activity
- CRP = C-reactive protein in mg/dL

## 7.4 Assessment of Safety

The safety profile of the IMP will be assessed through the recording, reporting, and analysis of baseline medical conditions, AEs, physical examination findings including vital signs and laboratory tests.

Comprehensive assessment of any apparent toxicity experienced by each patient will be performed from the time of giving informed consent and throughout the trial. The Investigator will report any AEs, whether observed by the Investigator or reported by the patient (see Section 7.4.2.2). The reporting period for AEs is described in Section 7.4.2.3.

### 7.4.1 Safety Monitoring Committee

An IDMC will review the safety data of this trial on ongoing basis (see Section 2). The IDMC is responsible for monitoring the safety of the trial participants and making appropriate recommendations based on the data reviewed. Details regarding the review process will be available in the relevant IDMC charter.

### 7.4.2 Adverse Events

#### 7.4.2.1 Adverse Event Definitions

##### Adverse Event

An AE is any untoward medical occurrence in a patient or clinical investigation patient administered a pharmaceutical product, regardless of causal relationship with this treatment. An AE can therefore be any unfavorable and unintended sign (including an abnormal laboratory finding), symptom, or disease temporally associated with the use of a medicinal product, whether or not considered related to the medicinal product.

For surgical or diagnostic procedures, the condition/illness leading to such a procedure is considered as the AE rather than the procedure itself.

Injection site pain during 3rd, 4th, and 5th injection administration will be reported as an AE similar to any injection site reactions at other time points of IMP administration.

The Investigator is required to grade the severity or toxicity of each AE.

Investigators will reference the National Cancer Institute – Common Terminology Criteria for AEs (NCI-CTCAE), version 4.03 (publication date: 14 June 2010), a descriptive terminology that can be used for AE reporting.

A general grading (severity/intensity; hereafter referred to as severity) scale is provided at the beginning of the above referenced document, and specific event grades are also provided.

If a particular AE's severity is not specifically graded by the guidance document, the Investigator is to use the general NCI-CTCAE definitions of Grade 1 through Grade 5 following his or her best medical judgment.

The 5 general grades are:

- Grade 1 or Mild
- Grade 2 or Moderate
- Grade 3 or Severe
- Grade 4 or Life-threatening
- Grade 5 or Death

Investigators must also systematically assess the causal relationship of AEs to IMP(s)/study treatment (including any other non-IMPs, radiation therapy, etc.) using the following definitions. Decisive factors for the assessment of causal relationship of an AE to the IMP include, but may not be limited to, temporal relationship between the AE and the IMP, known side effects of IMP, medical history, concomitant medication, course of the underlying disease, trial procedures.

**Unrelated:** Not reasonably related to the IMP. AE could not medically (pharmacologically/clinically) be attributed to the IMP under study in this clinical trial protocol. A reasonable alternative explanation must be available.

**Related:** Reasonably related to the IMP. AE could medically (pharmacologically/clinically) be attributed to the IMP under study in this clinical trial protocol.

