j For women of child-bearing potential only, a qualitative serum pregnancy test will be performed at screening and an on-site urine test performed at baseline; Weeks 4, 8, 12, 24, 36, 48, and 52; the ET visit and the safety follow-up visit. When there is no site visit, the patients will perform urine pregnancy tests themselves at home, ie, at Weeks 16, 20, 28, 32, 40, and 44.

k RF and ACPA will only be collected at screening.

- l Blood samples for human immunodeficiency virus, hepatitis B virus, and hepatitis C virus will be obtained at screening.
- m The tuberculosis Quantiferon-Gold test will only be performed in patients whose previous test was negative. Continuation of study medication will be excluded in patients who were QFT negative at randomization, but subsequently become QFT positive at Week 24.
- n If a bi-directional X-ray is available from the last 3 months before planned randomization, the exam will not be repeated at screening.
- o The ECG will be repeated at the ET or 4-week/4-month Safety/Follow-up visit only if in the opinion of the Investigator it is clinically warranted.
- p Patient reported outcome questionnaires and the Physician's Global Assessment of Disease Activity must be performed prior to any other assessments at all visits.
- q Performed locally.
- r All blood samples for immunogenicity assessment and IMP concentration must be drawn prior to administration of the IMP, which will be performed at the site for these visits. The date and exact time of sample collection must be recorded.
- s For assay validation purposes only, no result(s) will be reported.
- t Injection site pain (VAS) immediately post-injection, 15 min post-injection, and 1 hour post-injection. If the pain has not resolved by 1 hour post-injection, the patients will be asked to record when the pain resolves. Injection site pain during 3rd, 4th, and 5th injection will be reported as adverse event similar to any injection site reactions at other time point of IMP administration. The first 2 injections will be administered by qualified personnel. The next three doses of IMP (3-5) will be self-administered by the patient and injection site pain will be assessed. Pain will be recorded immediately after, 15 minutes after, and 1 hour after the injections received by the patient.
- u Injection site pain will be recorded by the patient at home.

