## 6.2

### Dosage and Administration

MSB11022-CCI [REDACTED] will be administered at a dose of 40 mg s.c. every other week starting from baseline up to and including Week 48.

The Humira® will be administered at a dose of 40 mg s.c. every other week starting from baseline up to and including Week 48.

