## 6.8 Assessment of Investigational Medicinal Product Compliance

The IMP will be administered at the site on the trial visit days defined in [Table 1](#). All other dosing will be done by the patient or patient's caregiver at home throughout the rest of the trial. Patients will be asked to record the date and time dispensed, date and time of dosing, location of administration, and injection site reaction (yes/no) in a patient diary. Diaries will be collected and reviewed at the trial visits specified in [Table 1](#).

Patients will be instructed to bring all IMP, including the used packaging, to each trial visit to allow for the assessment of compliance with trial treatment. Prior to discharge from each scheduled visit, patients will be given sufficient IMP for at-home dosing until the next scheduled visit.

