## Adverse Events of Special Interest

The AESIs have to be reported in an expedited manner (like the SAEs outlined above) using the AESI form.

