## Injection Site Pain

The patient's reported perception of pain will be measured on a VAS where the slash drawn by the patient represents pain of increasing intensity. The first 2 injections will be administered by qualified personnel. The next three doses of IMP (3-5) will be self-administered by the patient and injection site pain will be assessed. Pain will be recorded immediately after, 15 minutes after, and 1 hour after the injections received by the patient.

Results will be expressed in millimeters measured between the left end of the scale and the crossing point of the vertical line of the tick. This procedure is applicable for all VAS scales used in the trial.

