## 8 Statistics

### 8.1 Sample Size

According to EMA recommendation (EMA/CHMP/SAWP/200743/2016), a total of 100 patients/arm should be adequate for a study primarily focusing on safety. To account for drop outs, this descriptive study will include 260 randomized patients in total (130/arm) in order to ensure 200 subjects in the study at Week 52. In fact, based on averaged originator's dropout rates at Week 52, a 20% rate of drop-out overall is included in the sample size (29, 40, 41). This sample size will permit an informative assessment of the occurrence of most common AESI (> 1/10) such as injection site reactions, and rash with a precision of 12.0% and 9.0% for the AESIs incidence of 26.0% and 11.0% respectively (29).

A subset of 60 patients (30 per treatment arm) will be randomly selected to participate in population PK analysis.

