- Time since last study treatment administration to the study drug related injection site reaction start date/time calculated as the difference of the last study drug administration date/time and the study drug related injection site reaction start date/time divided by 3600 [(Injection site reaction start date/time Last study drug administration date/time)/3600]. Time since the last study treatment administration will not be calculated if study drug related injection site reaction start date or last study drug administration date are missing. If last study treatment administration time is missing then it will be set to 23:59. If injection site reaction start time is missing then it will be set to 00:00. In the special cases that any time is missing and last study treatment administration date equals injection site reaction start date then time since last study treatment administration will be set to 0. If a subject has more than one study drug related injection site reactions then the event with the shortest duration will be used.
- Number of subjects with time since the last study treatment administration to the injection site reaction <24 hours, ≥ 24 < 48 hours and ≥ 48 hours. If a subject has more than one study drug related injection site reactions then the event with the shortest duration will be used.
- Medication or procedure taken for study drug related injection site reactions. Frequencies and percentages will be based on the number of subjects.

Additionally the study drug related injection site reactions rate based on the overall number of study treatment injections administered will be calculated by SOC and PT.

The following frequency tales will be prepared by PT in order of decreasing frequency across both treatment arms:

- TEAEs with frequency of $\geq 5\%$ in any treatment arm
- TEAEs with frequency of $\geq 1\%$ in any treatment arm
- Treatment emergent AESIs (as per section 15.1).

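### Injection site pain solicited on the VAS at doses 3–5 is reported as an AE and pooled with other injection site reactions, which can dilute an arm difference in those reactions

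*Protocol*

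**What the plan says.** Protocol 7.4.2.1 (Adverse Event Definitions) states that pain at the third, fourth or fifth "injection administration will be reported as an AE similar to any injection site reactions at other time points of IMP administration". Table 1 footnote t gives the same rule directly after the VAS instructions. Protocol 7.7.2 sets the solicitation: "Pain will be recorded immediately after, 15 minutes after, and 1 hour after the injections received by the patient". Over three doses that is nine ratings per patient. Neither place gives a cut-off, a duration or a judgement step that links a rating to an AE. By contrast, 7.4.2.1 does set conditions before an abnormal laboratory or ECG finding counts as an AE.

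The other doses are also prompted, but less intensively. Under Protocol 6.8, patients dosing at home record the "location of administration, and injection site reaction (yes/no) in a patient diary". Under 7.4.2.2, patients are asked at each visit about changes in their condition.

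Injection site reactions carry weight in the plan. Protocol 8.1 bases its precision statement on the "occurrence of most common AESI (> 1/10) such as injection site reactions, and rash", with an incidence of 26.0% for the former. The pre-defined AESI itself, however, is hypersensitivity by narrow SMQ (Protocol 7.4.2.1, SAP 15.1).

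SAP 16.1.1 reports injection site reactions in several ways:

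- as a line in the overall AE summary;
- by SOC and preferred term, as local tolerability;
- for drug-related reactions, by grade with duration and by time since last dose;
- as a drug-related "injection site reactions rate based on the overall number of study treatment injections administered".

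SAP 16.6 tabulates them by ADA status. None of these separates pain at doses 3–5 from the rest. SAP 15.3.1.4 summarizes the VAS scores on their own.

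**The concern.** Pain is sought far more intensively at 3 doses than at the rest, and the resulting AEs enter the same tables. In a patient-level count of any injection site reaction, a patient who is already a case through prompted pain cannot become one again through another reaction. A difference between arms in other reactions is then compressed toward zero.

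Solicitation is blinded and identical in both arms, so it creates no obvious directional bias. But in a biosimilar comparison, dilution toward no difference is the reassuring direction, so symmetry alone does not answer the point. Protocol 3.3 and 5.2.1 also name injection site reactions as a clinical sign through which an immunogenicity difference might show. Dilution would weaken the table by ADA status in the same way.

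**Working it through.** **1. The plan's own figure.** Protocol 8.1 gives a precision of 12.0% at incidence 26.0% and 9.0% at 11.0%. Protocol 8.5.2 shows that this is the half width of the 95% CI for the difference between arms. With 1.96 × √(2p(1 − p)/n) and n = 100 per arm:

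- p = 0.26: 1.96 × √(2 × 0.26 × 0.74/100) = 12.2 points
- p = 0.11: 1.96 × √(2 × 0.11 × 0.89/100) = 8.7 points

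Both agree with the plan when rounded to whole points. The precision statement is sound for an event with a 26% incidence.

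**2. Doses affected.** Dosing is "40 mg s.c. every other week starting from baseline up to and including Week 48", so 48/2 + 1 = 25 doses. The VAS applies to 3 of them (12%), which leaves 22.

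**3. Dilution.** Let p be the share of patients with another injection site reaction. Let q be the share with prompted pain reported as an AE, equal in both arms and independent of other reactions.

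- Incidence of any reaction = 1 − (1 − p)(1 − q)
- Difference between arms = (p₂ − p₁)(1 − q)
- Share of cases in the arm with p = 0.26 who had prompted pain only = 0.74q/[1 − 0.74(1 − q)]

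The documents give neither q nor an expected difference. The table assumes p = 26% v 36% and shows a range for q. The half width takes both arms at the rate of the 26% arm, with 100 per arm.

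| q | Any reaction, 26% v 36% | Difference (points) | Prompted-only share of cases | Half width (points) |
|---|---|---|---|---|
| 0 | 26% v 36% | 10 | 0% | 12.2 |
| 0.1 | 33% v 42% | 9 | 22% | 13.1 |
| 0.3 | 48% v 55% | 7 | 46% | 13.9 |
| 0.5 | 63% v 68% | 5 | 59% | 13.4 |
| 0.7 | 78% v 81% | 3 | 67% | 11.5 |
| 0.9 | 93% v 94% | 1 | 72% | 7.3 |

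The half width moves little up to q = 0.5 and then narrows. The cost is attenuation of the difference, not loss of precision.

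**4. What q might mean per dose.** If a share r of patients report such pain at each dose, independently across doses, then q = 1 − (1 − r)³. This gives q = 14% at r = 5%, 27% at r = 10% and 49% at r = 20%. These values of r are also assumptions.

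**5. Other summaries.**

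- *Per-injection rate:* it pools 3 VAS doses with 22 others. The split by preferred term separates pain from other reactions, but not solicited from unsolicited pain.
- *Time since last dose:* for a subject with several drug-related reactions, the SAP keeps the shortest. Read as the shortest interval, a patient with drug-related prompted pain contributes about 0 hours, and any later-onset reaction in that patient drops out of the summary.
- *Duration:* the SAP keeps the longest event, so a longer reaction is not displaced. Pain-only patients still enter.
- *ADA-status table:* any count above preferred-term level is diluted as in step 3.

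**The case against.** The strongest reply is that the rule only says that collecting VAS scores does not exempt pain from ordinary AE reporting. An AE is an untoward medical occurrence that the Investigator must grade, and no sentence makes a VAS mark an AE. This is a fair reading, so a reader who infers that any mark above zero automatically qualifies goes further than the text. What stands is that the documents do not say which reading applies, and footnote t places the rule beside the VAS instruction without a threshold.

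Several further points also stand:

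- The other 22 doses are not unprompted. The diary item and the visit query narrow the contrast, although neither matches three ratings per dose.
- SAP 16.1 counts a subject once per preferred term, so a patient with prompted pain still appears in the row for, say, erythema. If pain is coded to its own term, it has its own row. Compression affects the patient-level any-reaction count, not those rows.
- Independence is an assumption. If pain and other reactions occur in the same patients, the relevant q is the share among patients without another reaction. That share is lower, and attenuation is smaller.
- Nothing says that the 26% excludes pain, so it may not be a pure rate of other reactions.
- Injection site pain is a named comparative objective. A real difference in pain is signal, so dropping it from the main tables would be wrong.

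A reader might also object that the same reading is counted twice, as a VAS score and as an AE. That is not a defect, because the two outputs are separate and no estimate adds them.

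**Conclusion.** The point holds as a gap in reporting and tabulation. Pain at doses 3–5 is solicited intensively and reported as an AE, no rule links rating to event, and the SAP pools it with other reactions. The patient-level incidence can exceed the 26% planning figure, and a difference in other reactions is multiplied by 1 − q. For an assumed 10 points, the loss runs from 1 point at q = 0.1 to 5 points at q = 0.5. These sizes rest on an assumed difference, an unknown q that is equal in both arms, and independence.

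Two stronger readings are tempting and are not supported. One is that prompted pain swamps the comparison. The documents give no rate of prompted pain, and at q = 0.1 the effect is small. The other is that the primary endpoint is compromised, or that every such pain event needs expedited AESI reporting. Protocol 5.2.3.1 and 8.1 do describe injection site reactions as common hypersensitivity events or AESIs. But the endpoint is defined by the narrow SMQ, and the documents do not show whether injection site pain falls within it. The SAP lists injection site reactions separately from AESIs.

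**What to change.** **SAP.** Keep the full injection site reaction tables. In 16.1.1 and 16.6, add a pre-specified summary in which a subject whose only event is injection site pain with onset on the day of dose 3, 4 or 5 is not counted as a case but stays in the denominator. Show those events on their own line by arm. Do the same in 15.1 only if injection site pain proves to fall within the narrow SMQ. Fix this before database lock and unblinding.

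**Protocol.** In 7.4.2.1 and Table 1 footnote t, clarify that a VAS mark alone is not an AE, and that pain at doses 3–5 is judged on the same basis as at other doses.

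**Cost.** One extra line per table, using AE onset and dosing dates already collected, plus a short protocol clarification. No event is hidden or removed from the listings. The onset-date rule cannot tell solicited from volunteered pain and sets aside some of the latter. For that reason it should be an added summary and not a replacement for the full count.

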### **Abnormal Laboratory Findings and Other Abnormal Investigational Findings**

Abnormal laboratory findings and other abnormal investigational findings (for example, on an ECG trace) should not be reported as AEs unless they are associated with clinical signs and symptoms, lead to treatment discontinuation or are considered otherwise medically important by the Investigator. If a laboratory abnormality fulfills these criteria, the identified medical condition (for example, anemia, increased ALT) must be reported as the AE rather than the abnormal value itself.

### **Serious Adverse Events**

An SAE is any untoward medical occurrence that at any dose:

- Results in death.
- Is life-threatening. (Note: The term "life-threatening" refers to an event in which the patient is at risk of death at the time of the event, not an event that hypothetically might have caused death if it was more severe.)

- Requires inpatient hospitalization or prolongs an existing hospitalization.
- Results in persistent or significant disability or incapacity.
- Is a congenital anomaly or birth defect.
- Is otherwise considered to be medically important. (Note: Important medical events that may not result in death, be life-threatening, or require hospitalization may be considered as SAEs when, based upon appropriate medical judgment, they may jeopardize the patient or may require medical or surgical intervention to prevent one of the outcomes listed above. Examples of such events include allergic bronchospasm requiring intensive treatment in an emergency room or at home, blood dyscrasias or convulsions that do not result in inpatient hospitalization, or the development of drug dependency or drug abuse.)

For the purposes of reporting, any suspected transmission of an infectious agent via an IMP is also considered an SAE, as described in Section [7.4.2.4](#).

